12.4.4 Patient Reported Outcomes (PRO) Objectives

Physical well-being, psychosocial well-being, sexual well-being, satisfaction with breast/nipples/abdomen, and satisfaction with overall outcome between the treatment arms at 24 months after radiation: Change in LBCQ and BLE scores at 24 months post-radiation (relative to pre-RT) and patient satisfaction scores as measured by the Breast Q overall outcome scale will be summarized and will be compared across the treatment arms using a two-sample t-test with a two-sided alternative. Linear mixed models will also be used to assess these scores longitudinally.

Patient satisfaction with trial participation by treatment arm as measured by the Was It Worth It Questionnaire at 24 months after radiation: Was It Worth It questionnaire responses to each of the five questions at 24 months will be summarized and will be compared across treatment arms using a Chi-square tests with a two-sided alternative. In particular, for questions 1-3, the proportion of patients who answered “yes” will be compared across the two treatment arms, and for questions 4 and 5, we will compare the proportion of patients who answered “it got worse” and “worse than I expected” (respectively) across the two arms.

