1.4 Patient Satisfaction and Well-being as Patient Reported Outcomes (PROs)

The assessment of patient-reported outcomes (PROs) in clinical research provides important insight into how therapies impact the daily lives of patients. There is a growing recognition that patient-reported endpoints are critical in oncology trials, particularly when cosmesis and toxicity are likely to be different in the treatment arms. Patient-reported adverse event collection has been shown to be more thorough than collection by provider-report, with consistent underreporting of side effects by providers.[69] Patient-reporting of health-related quality of life has become the gold standard in part because providers have been found to underestimate the pain and distress their patients are experiencing. [70-72]

In a trial of different radiation schedules, in which cosmesis may be substantially different in the two arms of the study, patient-reported satisfaction and well-being are particularly important. Although short-term differences between the treatment arms may be momentarily relevant to patients, the long-term cosmetic outcomes are most critical, so we have chosen to collect these data at 24 months (and compare to pre-treatment measures). In order to avoid burdening patients, we will not survey them for satisfaction or well-being in between these time points.

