G Breast Q Post Mastectomy questionnaire; unless already reconstructed, then Breast-Q Post Reconstruction.

H Only for patients who have had reconstruction

I Prior to RT, patients will be given the Patient Health Care Diary and the Health Care Expense Questionnaire (Appendix VII) to be returned to the clinic at the 2 to 8 week visit (see Section 10.7).

J After completion of RT, the patient will be given the Patient Health Care Utilization Diary (Appendix VIII) and will be asked to return it at the 12-month visit (see Section 10.7).

1 Need not be repeated if done within the past 30 days

2 To be completed at 6 months only. (up to 18 months, whenever reconstruction is completed, for BLE)

3 To be completed at 5 years only.

4 +/- 2 months

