Within patient satisfaction, there are three other scales: Satisfaction with breasts/nipples/abdomen, Satisfaction with overall outcome and Satisfaction with Care. There are three breast/nipple/abdomen satisfaction scales that are administered depending on the type of reconstruction: in the Satisfaction with breasts scale, there are questions regarding how comfortably bras fit, and how satisfied a woman is with her breast area both clothed and unclothed. There are also implant-specific items (e.g., amount of rippling that can be seen or felt). In the Satisfaction with nipples scale (to be completed only by those who underwent nipple reconstruction), there are items covering shape, color, projection and how natural the reconstructed nipple looks. In the Satisfaction with abdomen scale (to be completed only following autologous tissue breast reconstruction with TRAM or DIEP flap), there are items asking about overall appearance as well as position of navel (belly button) and scars. In the Satisfaction with outcome scale, there are items asking about whether or not expectations were met with respect to the aesthetic outcome and the impact reconstruction has had upon her life as well as satisfaction with the decision to have reconstruction (e.g. "I would do it again"). The Satisfaction with Care scale will not be included in this study.

Each scale can be used independently and scored separately. The BREAST-Q scoring software, QScore, transforms patient-reported data into summary scores ranging from 0-100 with a higher number meaning better quality of life or higher satisfaction on the various scales.

BREAST Q questionnaires are currently completed with pencil and paper. Patients will be asked to complete these at a clinic visit, but patients who are unable to receive and/or complete this survey in clinic will be allowed to receive and/or return this survey by mail.

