APPENDIX IX BOOKLET ADMINISTRATION SCHEDULE (ENGLISH): FOR SITE CONVENIENCE ONLY

Booklet Name	Booklet Contains	Booklet Schedule
BOOKLET A (Pre-reconstruction)	Includes Breast-Q survey(mastectomy postoperative module), LBCQ, and EQ-5D-3L	Complete prior to RT (mastectomy or TE only)
BOOKLET A (Post-Reconstruction)	Includes Breast-Q survey(reconstruction postoperative module), BLE, LBCQ, and EQ-5D-3L	Complete prior to RT (definitive reconstruction)
BOOKLET B	BLE, LBCQ , and EQ-5D-3L	Complete 6 months post RT (for BLE, when reconstruction completed, which may be up to 18 months out per protocol)
BOOKLET C	EQ-5D-3L	Complete 12 and 18 months post RT
BOOKLET D	Breast-Q (reconstruction postoperative module), BLE, LBCQ, EQ-5D-3L, and Was it Worth It (WIWI) Questionnaire	Complete 2 years post RT
BOOKLET E	Breast-Q (reconstruction postoperative module), BLE, and LBCQ	Complete 5 years post RT
BOOKLET F	Patient Health Care Expense Diary and Health Care Expense Questionnaire	Give the patient health care diary and health care expense questionnaire (Appendix VII) prior to RT and to be returned at the 2-8 week
BOOKLET G	Health Care Utilization Diary	Give the patient health care utilization diary after radiation therapy (Appendix VIII) and this is to be returned at the 12 month visit

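### Section 12.4.4 tests 24-month LBCQ (and BLE) as change from pre-RT with an unadjusted t-test and names no baseline-adjusted model, giving up precision that the data already collected would supply

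*Combined protocol and SAP*

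**What the plan says.** Section 12.4.4 assigns one test to the lymphedema questionnaires and BREAST-Q. For LBCQ and BLE the variable is "Change in LBCQ and BLE scores at 24 months post-radiation (relative to pre-RT"). For BREAST-Q it is "patient satisfaction scores as measured by the Breast Q overall outcome scale". Both are to be "compared across the treatment arms using a two-sample t-test with a two-sided alternative". The section then adds: "Linear mixed models will also be used to assess these scores longitudinally". It does not give that model's fixed effects, its handling of baseline or the contrast to be reported.

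On the purpose of the baseline, Section 1.4 says of the satisfaction and well-being data: "so we have chosen to collect these data at 24 months (and compare to pre-treatment measures").

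On what is collected before radiation:
- **LBCQ:** all patients (Section 5.0, Section 10.5.2, and both versions of Booklet A in Appendix IX).
- **BREAST-Q:** all patients, but the module varies: "G Breast Q Post Mastectomy questionnaire; unless already reconstructed, then Breast-Q Post Reconstruction".
- **BLE:** Section 10.5.2 offers it to all patients before radiation. Footnote H of the Study Calendar restricts it to patients who have had reconstruction. The Appendix IX booklet marked "Complete prior to RT (mastectomy or TE only") contains no BLE.

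Objective 2.5.1 lists five BREAST-Q domains to be compared at 24 months. The test sentence in 12.4.4 names only the overall outcome scale.

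**The concern.** A change score subtracts the whole baseline value, which fixes the regression slope of follow-up on baseline at 1. With equal SDs the true slope is the correlation, which is below 1, so the change score over-corrects and carries extra noise. When the correlation is below 0.5, it is noisier than ignoring baseline altogether. A baseline-adjusted model estimates the slope and avoids this.

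What is at stake is the width of the confidence intervals for patient-reported outcomes, which bear on the quality-of-life part of the second hypothesis in Section 1.6. Chance baseline differences between arms also carry into the change score. The plan already adjusts for baseline characteristics in the economic analyses (Section 12.4.5), so the idea is not foreign to it.

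**Working it through.** **Inputs.** The documents give no SD, correlation, power or alpha for any patient-reported comparison, so there is no plan figure for these outcomes to reproduce. The nearest is the sample size in Section 12.2: 396 evaluable per arm for the primary endpoint. That figure reproduces: (1.960 + 1.282)² × 2 × 0.25 × 0.75 / 0.10² ≈ 394.0, or 395 per arm after rounding up. I use 396 per arm for illustration; fewer patients may return questionnaires.

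Assumptions: the same SD, s, at both times; correlation r between pre-RT and 24 months of 0.3, 0.5 or 0.7; two-sided alpha 0.05.

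**Variance per patient entering the arm comparison.**
- Change score: 2s²(1 − r)
- 24-month score alone: s²
- ANCOVA: s²(1 − r²)

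**Extra patients needed to match ANCOVA.**
- Change score: 2(1 − r)/(1 − r²) − 1 = 2/(1 + r) − 1
- 24-month score alone: 1/(1 − r²) − 1

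| r | Change score | 24-month score alone |
|---|---|---|
| 0.3 | 2/1.3 − 1 = 54% | 1/0.91 − 1 = 10% |
| 0.5 | 2/1.5 − 1 = 33% | 1/0.75 − 1 = 33% |
| 0.7 | 2/1.7 − 1 = 18% | 1/0.51 − 1 = 96% |

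The first column applies to LBCQ, and to BLE where a baseline exists. The second applies to any BREAST-Q scale that has a baseline but is tested without it.

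**In SD units.** With 396 per arm and 80% power, the smallest detectable difference is (1.960 + 0.842) × √(2/396) = 0.199 SD for the 24-month score alone. Multiply by √(2(1 − r)) for the change score and by √(1 − r²) for ANCOVA:

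| r | Change score | ANCOVA |
|---|---|---|
| 0.3 | 0.236 | 0.190 |
| 0.5 | 0.199 | 0.172 |
| 0.7 | 0.154 | 0.142 |

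As power for a 0.2 SD difference at r = 0.5: 0.2 × √(396/2) = 2.814, giving about 80% for the change score. For ANCOVA, 2.814/√0.75 = 3.249, giving about 90%.

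**If the SDs differ.** Write s0 for the pre-RT SD and s1 for the 24-month SD. The change-score variance minus the ANCOVA variance is s0² + s1² − 2r·s0·s1 − s1²(1 − r²) = (s0 − r·s1)². This is never negative, so the direction of the result does not depend on equal SDs. Only its size does.

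**Which scales have a usable baseline.**
- *LBCQ:* yes, for all patients.
- *BREAST-Q psychosocial, chest and sexual well-being:* yes. Appendix II prints them in both modules with near-identical items, and every patient gets one module before radiation.
- *BREAST-Q overall outcome:* none shown. Section 10.4.1 explains that "In the Satisfaction with outcome scale, there are items asking about whether or not expectations were met with respect to the aesthetic outcome", so it concerns the result of reconstruction. It is printed in neither Appendix II module.
- *BLE:* unresolved. Under footnote H and Appendix IX, patients awaiting reconstruction have no pre-RT score. Section 4.6 classes everyone with only a temporary expander as delayed. For these patients neither a change score nor an ANCOVA can be computed.

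**The case against.** The strongest reply has four parts.

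First, the t-tests are valid. Randomization makes the change score and the raw 24-month score unbiased, and no power is claimed for these secondary outcomes. This stands: the issue is efficiency and protection against chance imbalance, not error control.

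Second, the mixed models already planned could recover most of the precision. This is partly right. A model with pre-RT score as an outcome and a common pre-RT mean would do so. But 12.4.4 does not specify that, and the companion model in 12.4.3 takes changes as its outcome. Section 12.6 brings in covariates only if more than 5% of data are missing and the mechanism is judged MCAR or MAR. The reply softens the point without removing it.

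Third, a reader might infer that every baseline needed is already in hand, so that the same loss applies to BREAST-Q as tested. The documents do not support this. The one BREAST-Q scale assigned to a test has no pre-RT score shown, and pre-RT BLE is in conflict between sections. The 54% to 18% range belongs to change scores only.

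Fourth, a reader might infer that these tests decide whether hypofractionation reduces lymphedema. They do not. Objective 2.4.1 concerns arm lymphedema incidence, which Section 12.4.3 tests through arm volume.

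**Conclusion.** The point holds for LBCQ: a pre-RT score is planned for every patient, and the named test uses it inefficiently. Under equal SDs and r between 0.3 and 0.7, the cost is equivalent to 54% down to 18% more patients. Both assumptions come from this review, since the documents give no values. The direction does not depend on them, but the size does.

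The point extends to the three BREAST-Q well-being scales shared by both modules. Objective 2.5.1 requires them to be compared, but 12.4.4 names no test for them. If they were tested at 24 months without baseline, the cost would be about 10% to 96% over the same range of r. It does not extend to the overall outcome scale.

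For BLE, the uncertainty over who has a pre-RT score matters more than the lost precision: under footnote H and Appendix IX, a change-score test leaves out delayed-reconstruction patients. Overall this is a modest improvement to secondary analyses, worth making because it needs no new patients.

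**What to change.** 1. **LBCQ.** Replace the change-score t-test with an ANCOVA of the 24-month score on arm, pre-RT LBCQ and the two stratification factors (type and timing of reconstruction). Alternatively, take the 24-month contrast from the planned mixed model, with pre-RT score as an outcome and one pre-RT mean for both arms. Report the adjusted difference with its 95% CI.
2. **BREAST-Q.** State the same analysis for the psychosocial, chest and sexual well-being scales. Leave the overall outcome scale as an unadjusted 24-month comparison.
3. **BLE.** Reconcile Section 10.5.2 with footnote H of the Study Calendar and Appendix IX. If pre-RT BLE is limited to reconstructed patients, use the common-baseline mixed model with timing of reconstruction as a term, because timing determines who has a baseline. This keeps delayed-reconstruction patients in the analysis, though they gain no precision from a baseline they do not have.
4. **Mixed model.** Write down its outcome vector, fixed effects, covariance structure and target contrast.

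The cost is analysis wording, to be settled before the comparative data are seen. LBCQ and the shared BREAST-Q scales need no further data collection.

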12.4.5 Economic Analyses

Direct costs of medical care to each patient will be estimated using utilization information from the health care expense survey and the health care utilization survey, along with publicly available Medicare reimbursement rates. In particular, based on the reported number of outpatient visits to the radiation oncologist, medical oncologist, surgeon who performed mastectomy, plastic surgeon or physical therapist, and the number of visits to the emergency room, the number of hospital admissions (and the days per each hospital admission), and the number of surgical procedures to breast reconstruction (along with the names of the procedures), Medicare reimbursement rates can be used to estimate what the direct cost to each patient would be if that patient were covered by Medicare. Generalized linear models will then be used to model these costs as a function of treatment, time on study, and all available baseline patient characteristics to assess the extent to which estimated direct cost is impacted by the type of radiation dosing. Given the well-known fact that healthcare costs are typically highly skewed, regression models will employ the appropriate distribution and transformation link. We will also assess the degree to which indirect costs differ across the two treatment arms. Specifically, using information from the phone survey, along with information on work status prior to breast cancer diagnosis, the average number of days worked per week (at baseline), and the average number of hours worked per day (at baseline), we will estimate the hours of work missed and the total distance traveled to receive radiation treatment for each patient. These two endpoints will be modeled (separately) as a function of treatment, time on study, and all available baseline patient characteristics to assess the extent to which the treatment arms differ with respect to indirect cost.

In addition to using them to estimate direct costs, the health care utilization measures (number of outpatient visits to the radiation oncologist, medical oncologist, surgeon who performed mastectomy, plastic surgeon, physical therapist; the number of visits to the emergency room, the number of hospital admissions, the days per each hospital admission, and the number of surgical procedures to breast reconstruction) will be compared (separately) across the two dosing arms. Given that these outcomes are counts, appropriate count regression models (e.g., poisson regression, negative binomial regression or zero-inflated negative binomial regression) will be used to account for any residual imbalance between the study arms following randomization.

EQ-5D survey results for the baseline and follow-up will be presented in three ways: (i) the descriptive system on the 5 dimensions will reflect the patients general health profile; (ii) EQ-VAS will represent patients' self-reported health status; and (iii) the summary measure of generic health status in terms of EQ-5D-3L index value. In order to obtain the last measure, EQ-5D responses representing specific health state will be converted to a single index value using the EQ-5D-3L value sets for the U.S. This, along with the survival data, will then be used to estimate the effectiveness measure in our cost-effectiveness analysis, that is, quality adjusted life year or QALY. Mean QALYs between interventions will be compared using two-sided t-test. Cost-effectiveness will be assessed and compared in terms of incremental cost-effectiveness ratio or ICER, that is, US dollars per QALY between the interventions. Costs associated with each of the interventions will be estimated. For healthcare utilizations mentioned above, costs will be imputed from the literature. Extensive sensitivity analyses will be conducted to document sensitivity of the final results to any of the imputed cost parameters.

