2.6 Economic Analysis

- 2.6.1** To compare the direct and indirect patient costs for radiation therapy by treatment arm.
- 2.6.2** To compare patient reported total health care service utilization 12 months after the completion of radiation.
- 2.6.3** To compare the economic impact of treatment.

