7.4 Radiotherapy

All radiation therapy questions should be directed to the Alliance A221505 Radiation Co-Chairs.

The radiation methods and dose volume parameters are adapted from RTOG criteria, as outlined in the RTOG breast atlas: [REDACTED]

Radiation therapy treatment planning should begin after consultation with the radiation oncologist and prior to radiation treatment.

A deviation unacceptable will be scored for failure to prescribe proper dose and not treating the required regional lymph nodes, including IMs.

The use of a radiation chest wall or scar boost is not allowed on this trial. If the radiation oncologist feels that a particular patient must receive a scar boost, she should not be enrolled on this trial. Use of a scar boost on an enrolled patient will be scored as a deviation unacceptable, but these patients will still be followed.

Every attempt should be made to meet dose constraints. If dose constraints are not met, patients will remain on protocol treatment unless in unusual circumstances it is recommended that they be removed from protocol treatment by a radiation co-chair. It is recommended this be discussed with a radiation co-chair prior to starting radiation.

Patients will be registered after mastectomy and randomized to one of the following study treatment arms:

Arm 1: Conventional fractionation radiation to the chest wall or reconstructed breast, supraclavicular fossa, axilla and internal mammary nodal basin. 50 Gy in 25 daily 2 Gy fractions. Treatment will be given 5 days a week for 5-6 weeks (no treatment weekends and holidays).

Arm 2: Hypofractionated radiation to the chest wall or reconstructed breast, supraclavicular fossa, axilla and internal mammary nodal basin. 42.56 Gy in 16 daily 2.66 Gy fractions. Treatment will be given 5 days a week for 3-4 weeks (no treatment weekends and holidays).

In the case of a departmental holiday, RT may be given 4 days a week. In case of medical illness or RT side effect(s), treatment breaks are allowed as needed per standard practice.

For both randomized treatment arms, radiation is to be delivered to the following planning target volumes: the reconstructed breast/chest wall, undissected axilla*, supraclavicular fossa and internal mammary nodal chain in the first 3 intercostal spaces.

* The undissected axilla typically includes the high level II and Level III nodes. If an axillary dissection has been performed, RT will only be directed to the un-dissected axilla.

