11.0 END OF TREATMENT/INTERVENTION

11.1 Duration of Treatment

Radiation therapy is to be given 5 days a week for 5-6 weeks in Arm 1 and 5 days a week for 3-4 weeks in Arm 2, per [Section 7.4](#).

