(If no), which of the follow apply (check one):

☐ I was in a health care facility during radiation

☐ I was living with a friend/family member during radiation (answer the commuting questions above and below as applicable)

☐ I stayed hotel, apartment, or similar facility during radiation (answer the commuting questions above and below as applicable)

If hotel, apartment or similar facility, estimated cost of lodging during your radiation treatment \$ __ __ __ __

(If yes), method of transport used to get to the radiation therapy facility (Check all that apply)

Car ☐ Yes ☐ No

(If yes) approximate cost for parking per visit \$ __ __ . __ __

Did you drive yourself? ☐ Yes ☐ No

Were you driven? ☐ Yes ☐ No

Was it a combination of driving yourself or being driven ☐Yes ☐No
Shuttle ☐Yes ☐No

(If yes) Approximate cost per visit \$ __ __ . __ __

Public transport ☐Yes ☐No

(If yes) Approximate cost per visit \$ __ __ . __ __

On foot ☐Yes ☐No

Taxi/car service ☐Yes ☐No

(If yes) Approximate cost per visit (both ways) \$ __ __ __

Number of radiation treatments during which at least one other person accompanied patient __ __

Number of visits to radiation treatment facility since completing radiation therapy (follow up visits) __ __

From the 1st day of starting radiation, until 40 days after the completion of radiation:

Number of days the patient was unable to go to work at all __ __

Number of days the patient went to work part-time __ __

If part time, number of hours reduced from typical work day __ __

Estimate child care costs due to radiation therapy \$ __ , __ __ __

Estimate wages lost due to radiation therapy \$ __ __ , __ __ __

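### The direct-cost, work-missed and travel models adjust the arm comparison for time on study, an undefined post-randomisation variable, so the treatment coefficient need not be the cost difference by arm

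*Combined protocol and SAP*

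**What the plan says.** Objective 2.6.1 is "To compare the direct and indirect patient costs for radiation therapy by treatment arm". Section 12.4.5 serves it with regression models. For direct cost, "Generalized linear models will then be used to model these costs as a function of treatment, time on study, and all available baseline patient characteristics", with a distribution and link chosen for skewed data. For hours of work missed and total distance travelled for radiation, "These two endpoints will be modeled (separately) as a function of treatment, time on study, and all available baseline patient characteristics". The stated aim in both places is to judge how far cost depends on the radiation schedule.

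No section gives time on study a start, an end or a functional form (covariate or offset). The count models for health care use, later in 12.4.5, do not mention it.

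Four other places bear on what it could mean:
- **Length of radiation.** Section 7.4 gives "50 Gy in 25 daily 2 Gy fractions" in Arm 1 and "42.56 Gy in 16 daily 2.66 Gy fractions" in Arm 2. Section 11.1 gives "5 days a week for 5-6 weeks in Arm 1 and 5 days a week for 3-4 weeks in Arm 2".
- **Missed-work recall.** The Health Care Expense Questionnaire (Appendix VII) asks about the period "From the 1st day of starting radiation, until 40 days after the completion of radiation".
- **Other cost windows.** Under section 10.7, billing-code charges run from registration to 12 months after radiation. The utilization diary runs from the end of radiation to 12 months.
- **End of follow-up.** Sections 11.3.1 and 11.3.2 end it at recurrence, contralateral or other new cancer, or alternative treatment, with a maximum of 15 years after radiation.

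**The concern.** A comparison by randomised arm asks for the total effect of assignment. A covariate fixed before randomisation leaves that target intact in a linear model; one that arises afterwards need not. If the covariate differs between arms and predicts the outcome, the treatment coefficient becomes the difference between patients with equal time on study, which is another question.

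Two features of this trial make that possible. Any clock that starts at registration or at the first fraction and stops at a milestone after radiation contains the course, and the course is shorter in Arm 2. Section 10.7 expects the saving to come from fewer treatment visits and an earlier return to normal activity, so such a clock carries part of the mechanism. Follow-up can also end early because of events that may themselves be costly. The estimate would then depend partly on who stopped and why.

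Because the term is undefined, the same sentence permits analyses with quite different answers, and the choice could be made after the data are seen.

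**Working it through.** Section 12.4.5 states no effect size, cost level or power, so there is no figure of the plan's own to reproduce. The check asks how much the arm contrast moves under different definitions of time on study.

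**1. Arm difference in the length of radiation.** Inputs: 25 and 16 weekday fractions (section 7.4), with no holidays or breaks. A Monday start gives 33 and 22 calendar days; any other weekday start gives 35 and 22. Averages: (33 + 4 × 35)/5 = 34.6 days and 22.0 days. The difference is 11 to 13 days, mean 12.6.

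**2. Linear identity.** Adjusted arm effect = unadjusted effect − b × (mean time in Arm 2 − mean time in Arm 1), where b is the pooled within-arm slope of the outcome on time. With a clock that contains radiation, the time difference is −12.6 days. A positive b shrinks the saving, a negative b enlarges it, and b = 0 leaves it alone.

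**3. Log link with time as an offset.** The arm ratio is multiplied by (34.6 + k)/(22.0 + k), where k is the number of days of follow-up after radiation. Take 16/25 = 0.64 as the true ratio, as for distance among completers:

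| Clock | Multiplier | 0.64 becomes |
|---|---|---|
| Radiation only | 1.573 | 1.01 |
| Radiation + 40 days | 1.203 | 0.77 |
| To 12 months after | 1.033 | 0.66 |
| To 24 months after | 1.017 | 0.65 |
| To 5 years after | 1.007 | 0.644 |

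**4. Simulation of the covariate form.** Least squares, 396 per arm, 300 replicates. Assumptions not in the documents: 40% of working days missed on average during radiation, a quarter of that rate in the next 40 days, 300 cost units per fraction, 20 units per day throughout, about 10% dropout a year, and a mean of 1.5 break days. With no early stopping of radiation, the share of the saving kept was:

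| Clock | Missed work | Distance | Direct cost |
|---|---|---|---|
| Radiation + 40 days | 0% | 104% | 94% |
| Registration to 12 months after | 100% | 100% | 92% |
| Registration to last contact, 2–5 years | 100% | 100% | 99% |
| End of radiation to 12 months | 100% | 100% | 100% |

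The identity explains the rows.
- *Missed work, radiation + 40 days.* The unadjusted saving is 0.4 × (5/7) × 12.6 = 3.6 days. The within-arm slope is 0.4 × 5/7 per day, so the correction is also 3.6 days and nothing is left.
- *Direct cost, registration to 12 months.* The saving falls from 2,963 to 2,734 units, and 229/2,963 = 8%.
- *Distance.* Among completers the number of fractions is fixed within arm, so b is about zero. The departures from 100% in the first row are simulation noise. If 2% or 5% stop radiation early, a radiation-based clock keeps only 29% or 13 to 14% of the distance saving, and 24 to 31% or 13 to 14% of the direct-cost saving.

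**5. Sensitivity to follow-up cost and to costly early stoppers.** Let r be daily cost in follow-up divided by daily cost during radiation. On a clock from the start of radiation to 12 months after it, with 8% stopping follow-up early (assumption), the share of the direct-cost saving removed is close to r. The 8% in step 4 fits this, since 20/(300 × 25/34.6 + 20) = 0.084. A lump cost for early stoppers, in radiation-day units (also an assumption), gives these shares removed:

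| r | No lump | 20 units | 40 units |
|---|---|---|---|
| 0.05 | 5% | −2% | −9% |
| 0.10 | 10% | 3% | −4% |
| 0.20 | 20% | 13% | 6% |

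Negative values mean that the saving is exaggerated. With r = 0.50 and no lump, about half is removed.

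**The case against.** The best defence is that time on study was meant as a routine adjustment for unequal follow-up. On the readings that the phrase most naturally suggests, it would do little harm: registration to last contact over several years costs 0 to 1% of each saving, and a clock starting at the end of radiation costs nothing. The large losses need a clock equal to the radiation course or to the recall window. The utilization diary, which feeds the direct-cost estimate, starts after radiation. The count models compare utilization by arm without the term, so that comparison stands outside the criticism. Section 12.6 also provides for examining missingness above 5%. Finally, step 4 uses least squares, whereas the plan calls for generalized linear models suited to skewed costs.

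Much of this stands. A reader might infer that the shorter schedule itself reduces time on study, and that the planned models will therefore shrink the saving. The documents do not support that. With no definition, the link to the schedule is conditional, and the direction can reverse if early stoppers are costly. Nor does a rule that the share lost is about r carry over to missed work. That outcome is recalled only to 40 days after radiation, and on a 12-month clock its saving was fully kept.

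What the defence does not meet is the rule itself. The plan commits to conditioning on a post-randomisation variable and gives no reason for it. Section 12.6 is written around patient-reported outcomes and does not say how truncated cost records are handled. Conditioning on observed time does not correct for stopping that depends on costly events.

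**Conclusion.** The point holds in a conditional form. All three models include an undefined post-randomisation covariate, while the objective is the difference by randomised arm. The treatment coefficient departs from that target whenever time on study differs by arm and predicts the outcome.

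The documents fix only one quantity, the extra 11 to 13 days of radiation in Arm 1. The rest rests on the assumptions stated above. At those cost levels the loss is 0 to 8% on registration-to-12-month or multi-year clocks. It reaches nearly all of the missed-work saving if the clock is the radiation-plus-40-day window. The direct-cost loss rises with the daily cost of follow-up and can turn into an exaggerated saving if early stoppers are expensive. Distance among patients who complete radiation is little affected.

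The primary endpoint is untouched. The change is worth making because the present wording allows materially different answers to objective 2.6.1.

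**What to change.** In section 12.4.5:
- Remove time on study from the main models for direct cost, hours missed and distance. Keep treatment, the two stratification factors and the baseline covariates.
- State a fixed cost window for each outcome, for example registration to 12 months after radiation for direct cost and the existing recall window for missed work.
- For direct cost, handle records that stop early by inverse-probability-of-censoring weighting or by multiple imputation within arm.
- If time on study is kept at all, define its start, its end and whether it is a covariate or an offset, and confine it to a sensitivity analysis.

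The cost is a wording change and modest programming, with no new data collection. Intervals for direct cost may be slightly wider because of the weighting or imputation.
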